5.3.2 Analysis of Secondary Endpoints

Continuous outcomes

Linear models (ANCOVA) will be used with the following variables:

- Dependent variables:
 - AUC value based on DESS scores week 14 till week 52, i.e., assessed at FU1-FU3
 - Change from baseline (t1) of patient-reported stress scores based on PSS-10 scores at t9 (12 weeks after t1)

- Change from baseline (t1) of patient-reported state-anxiety scores based on STADI scores at t9 (12 weeks after t1)
- Independent variables:
 - Random group as two factors (i.e. 1st factor: treatment discontinuation vs continuation; 2nd factor; high vs. medium expectation) and their interaction
 - The stratification variables of the randomization process:
 - *intake duration with 24 months as a marker for long-term intake (<24 months of AM vs. >24 months)*
 - *risk of developing discontinuation symptoms associated with the antidepressant medication (moderate vs. higher or unknown risk)*
 - Concerning secondary endpoint a), the corresponding pseudo baseline value (t1) will additionally be included as covariate.

Primary interest lies in the interaction between the two factors describing the random group. The post-hoc comparisons between the subgroups will be addressed exploratively. If the corresponding p-value (for the interaction) is >0.15 the model will be calculated without the interaction and the independent main effects of the 2 factors will be assessed.

Normal distribution of the residuals will be checked graphically via a histogram of residuals. If the assumption of normally distributed residuals is clearly violated, a sensitivity analysis using the log-transformation for the dependent variable will be performed to judge the robustness of the results. Adjusted mean values and adjusted effect estimators (mean differences) with corresponding 95%-Wald confidence intervals and p-values will be given.

The ICC (intra-class correlation) will also be reported, where appropriate.

Linear mixed model (random intercept model) will be used with the following variables:

- Dependent variable:
 - Bias score (emotional versus neutral faces, measured in ms)
- Independent variables (fixed factors):
 - Expectation concerning recurrence of discontinuation symptoms derived from the factors of the random group: high expectation (open discontinuation group) versus moderate expectation (both hidden groups, continuation and discontinuation) versus low expectation (open continuation group)
 - Type of emotion (happy versus sad versus fearful)
 - 3x3 interaction of expectation and emotion
 - The stratification variables of the randomization process:
 - *intake duration with 24 months as a marker for long-term intake (<24 months of AM vs. >24 months)*
 - *risk of developing discontinuation symptoms associated with the antidepressant medication (moderate vs. higher or unknown risk)*
- Variable used as random effect (intercept)
 - Patient ID

Primary interest lies in the interaction between expectation and emotion. The post-hoc comparisons between the expectation - subgroups regarding the different emotions will be addressed exploratively. If the corresponding p-value (for the interaction) is >0.15 (i.e. the expectation groups do not differ substantially regarding the different emotions) the model will be calculated without the interaction

and the independent main effects of the 2 factors will be assessed (again with post-hoc comparisons if appropriate).

Adjusted mean values and adjusted effect estimators (mean differences) with corresponding 95%-Wald confidence intervals and p-values will be given.

The ICC (intra-class correlation) will also be reported, where appropriate.

Binary outcome

Binary logistic model will be used with the following variables:

- Dependent variable:
 - Binary variable judging any recurrence of depression during 13 week experimental period (i.e. yes/no) at t9
- Independent variables:
 - Random group as two factors (i.e. 1st factor: treatment discontinuation vs continuation; 2nd factor; high vs. medium expectation) and their interaction
 - The stratification variables of the randomization process:
 - *intake duration with 24 months as a marker for long-term intake (<24 months of AM vs. >24 months),*
 - *risk of developing discontinuation symptoms associated with the antidepressant medication (moderate vs. higher or unknown risk)*

Primary interest lies in the interaction between the two factors describing the random group. The post-hoc comparisons between the subgroups will be addressed exploratively.

Again, a model without the interaction term of the random group-factors but only the 2 main factors is calculated if the corresponding interaction p-value is above 0.15.

Rates and adjusted effect estimators (odds ratios) with corresponding 95%-Wald confidence intervals and p-values will be given.

Time-to-event outcome

A Cox proportional hazards model will be used for the endpoint first recurrence over the course of the clinical trial. Independent variables are:

- Random group as two factors (i.e. 1st factor: treatment discontinuation vs continuation; 2nd factor; high vs. medium expectation) and their interaction
- The stratification variables:
 - intake duration with 24 months as a marker for long-term intake (<24 months of AM vs. >24 months),
 - risk of developing discontinuation symptoms associated with the antidepressant medication (moderate vs. higher or unknown risk)

Primary interest lies in the interaction between the two factors describing the random group. The post-hoc comparisons between the subgroups will be addressed exploratively.

If the corresponding p-value (for the interaction) is >0.15 the model will be calculated without the interaction and the independent main effects of the 2 factors will be assessed.

The proportional hazards assumption will be checked graphically via Schoenfeld residuals.

Event rates and adjusted effect estimators (hazard ratios) with corresponding 95%-Wald confidence intervals and p-values will be given.

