2.3 Sample Size

A medium effect size of $f=0.22$, a significance level of $\alpha=0.05$, and a power of 80% were assumed. This resulted in 168 patients needed in total (i.e. 42 per group) using an ANOVA model (with main effects and interactions). Furthermore, with an expected drop-out rate of at most 15%, in total 196 patients need to be recruited (i.e. 49 per group).

Sample size calculation was conducted using G*Power (version 3.1.9.2).

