2.4 Framework

Test for difference will be applied for all endpoints. The primary endpoint is tested in confirmatory manner. A significance level of 0.05 will be used. All secondary and safety endpoints will be analysed in an exploratory way and thus, no adjustment for multiplicity will be applied.

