2.6 Timing of Outcome Assessments

See Table 1.

Table 1. Schedule of enrolment, intervention and assessments according to SPIRIT-PRO.

	STUDY PERIOD								
	Enrolment		Allocation	Experimental phase			Clinical observation		
Timepoint	S1	S2	t0	t1-t5	t6-t8	T9	FU1	FU2	FU3
Weeks	-2	-1	0	1/2/3/4/5	7/9/11	13	26	39	52
Enrolment									
Eligibility screen	✓	✓							
Informed consent			✓						
Initial consultation prescribing physician			✓						
Randomization				✓					
Interventions					✓	✓	✓		

Discontinuation versus continuation of AM High versus moderate expectation (open versus hidden treatment)			✓ ✓	✓ ✓	✓ ✓	
Assessment						
Primary outcome measures						
Discontinuation symptom load (DESS)		✓	✓	✓	✓	
Secondary outcome measures						
Discontinuation symptom load (DESS)					✓	✓
Recurrence			✓	✓	✓	✓
Psychophysiological stress (PSS-10)*		✓			✓	
State anxiety (STADI State)*		✓			✓	
Attentional, affective processing (Posner task)*					✓	
Possible modulators						
Psychophysiological stress (PSS-10)*		✓				
Side effects of antidepressant medication (GASE*)		✓			✓	
Prior discontinuation experience (GEEE _{PRE} *)		✓				
Personality traits (BFI-10)*		✓				
Trait anxiety (STADI State)*		✓				
Somatosensory amplification (SSAS)*		✓				
Illness perception (single item)		✓				
Further assessments						
Optional: rsfMRI		✓	✓ (t1)			
AM blood serum level			✓(t1)		✓	
Trait marker stress*		✓				
Adherence (single item)		✓	✓	✓	✓	✓
Self-reported depressive symptoms (BDI-II)*	✓	✓	✓	✓	✓	✓
Expert-rated depressive symptoms (MADRS)*	✓	✓	✓	✓	✓	✓
Prior discontinuation symptoms (DESS _{PAST})		✓				
Current treatment effects (GEEE _{ACT} *)		✓	✓	✓	✓	✓
Expectations (TEX-Q*)		✓	✓	✓	✓	✓
Expectations (GEEE _{EXP} *)		✓	✓	✓	✓	✓
Behavioral inhibition/approach (BIS-BAS scale)*		✓				
Psychopathology (SCID-5-CV interview)*	✓					
Well-being (SWEMWBS)		✓	✓	✓	✓	✓
Depression and Anxiety (PHQ-4)					✓	✓
Subjective Impairment (PDI*)		✓	✓(t1,t5)		✓	
Substance Use & Coping			✓(t1,t5)	✓(t7)	✓	
Screener Warmth & Competence*		✓	✓(t5)		✓	
Adverse events (single safety items)		✓	✓	✓	✓	✓
Suspicions about treatment (GEEE _{END})*					✓	
Demographic* & medical characteristics		✓			✓	✓
Debriefing & close-out						
Debriefing					✓	
Consultation prescribing physician					✓	
Individualized discontinuation plan for continuation groups						✓

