- d) Change from baseline (t1) in patient-reported stress at t9 (12 weeks after t1), assessed with the Perceived Stress Scale (PSS-10; Cohen et al. 1983; Klein et al. 2016). The PSS-10 includes ten items with five response options (0 'none of the time' to 5 'very often'). Total scores range between 0-40, with higher sum scores indicating higher perceived stress. Difference scores will be calculated by subtracting total scores at t1 from total scores at t9, resulting in a range from -40 to 40, with higher scores indicating increased stress.
- e) Change from baseline (t1) in patient-reported state anxiety at t9 (12 weeks after t1), assessed with the two anxiety-related state subscales of the *State-Trait-Anxiety-Depression-Inventory* (STADI; Laux et al. 2016, Renner et al. 2018). Each includes 5 statements with four response options (1-4). Total state-anxiety scores base on sum scores of both anxiety subscales and range between 10 and 40, with higher sum scores indicating higher trait anxiety. Difference

scores will be calculated by subtracting total scores at t1 from total scores at t9, resulting in a range from -30 to 30, with higher scores indicating increased state-anxiety.

f) Bias scores of the emotional Posner task (Brassen et al., 2011) are the differences between reaction times to emotional faces and neutral.

In short, participants respond as fast as possible to a dot target by button pressing, while neutral, happy, sad, or fearful faces are presented as distractors. Targets are preceded by either spatially-directing cues leading to covert shifts in the attentional focus (i.e., low attentional resources to process distractors) or non-spatial cues, leaving the attentional focus on the faces. We will measure reaction times in milliseconds (ms) for each condition and calculate difference scores between the reaction times to happy and neutral faces, sad and neutral faces, as well as fearful and neutral faces under high attention to faces.

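### The stress and state-anxiety changes are analysed without their baseline score, and the log fallback prescribed for them does not exist for zero or negative changes

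*SAP*

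**What the plan says.** SAP 5.1.2 defines endpoint d) as the change in PSS-10 from t1 to t9: "Difference scores will be calculated by subtracting total scores at t1 from total scores at t9, resulting in a range from -40 to 40". Endpoint e), the change in STADI state anxiety, is formed in the same way, "resulting in a range from -30 to 30, with higher scores indicating increased state-anxiety".

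SAP 5.3.2 puts both changes, together with the follow-up DESS AUC (endpoint a), under linear models labelled ANCOVA. The terms common to all three are the two group factors, their interaction and the two stratification variables. The baseline score is then added for one of them only: "Concerning secondary endpoint a), the corresponding pseudo baseline value (t1) will additionally be included as covariate". The primary model in 5.3.1 also includes the t1 value.

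For clearly non-normal residuals, 5.3.2 says of these models that "a sensitivity analysis using the log-transformation for the dependent variable will be performed to judge the robustness of the results". It gives no offset and no exception for change scores. Section 5.4 repeats the log re-analysis with a qualifier about appropriateness, but that sentence concerns the primary analysis only.

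On status, 2.4 is clear: "All secondary and safety endpoints will be analysed in an exploratory way".

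**The concern.** Two separate problems sit in the same block of 5.3.2.

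First, subtracting the baseline is not the same as adjusting for it. The two agree only if the slope of the t9 score on the t1 score is 1. At any other slope the change score leaves part of the baseline variation in the residual, and a chance baseline difference between groups passes into the estimated effect. The SAP adjusts for t1 in the primary model and for endpoint a), and gives no reason for omitting it for d) and e). The loss falls on the interaction, which 5.3.2 names as the main interest and which is the least precise contrast in a 2x2 design.

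Second, a prespecified fallback has to be computable when it is triggered. Taking the log of a change that may be zero or negative is not. If the software silently drops those patients, the check runs only on people whose stress or anxiety rose, which is selection on the outcome. An offset chosen afterwards would be data-driven.

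**Working it through.** **Inputs from the SAP.** 42 per group, 168 in total, f = 0.22, two-sided 5%, 80% power (2.3, 3.1); ranges of the changes (5.1.2); model terms (5.3.2). **Assumed, because the SAP gives no value:** the within-group t1-t9 correlation ρ, and k = SD(t9)/SD(t1).

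**The plan's own figure.** The SAP's only power figure is the total of 168. A noncentral F with 1 numerator df, 4 groups and λ = f²N reaches 80% power at N = 165, which rounds up to 168 for four equal groups; power at 168 is 80.9%. The figure is reproduced. The SAP states no power for d) or e).

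**Residual variance**, in units of SD(t1)²:

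- change score, no baseline: 1 + k² − 2ρk
- baseline-adjusted: k²(1 − ρ²)
- difference: (1 − ρk)², which cannot be negative and is zero only when the slope ρk equals 1

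Example at k = 1, ρ = 0.5: 1.00 against 0.75, a difference of 0.25 = (1 − 0.5)².

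Ratio, adjusted to unadjusted:

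| k | ρ = 0.3 | ρ = 0.5 | ρ = 0.7 |
|---|---|---|---|
| 0.8 | 0.50 | 0.57 | 0.63 |
| 1.0 | 0.65 | 0.75 | 0.85 |
| 1.2 | 0.76 | 0.87 | 0.97 |
| 1.4 | 0.84 | 0.94 | 1.00 |

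Interval width scales with the square root: √0.50 = 0.71, so 29% narrower at one corner, and 0% narrower at the other. The extra degree of freedom costs a factor of about 1 + 1/160 = 1.006, or 0.6% of variance.

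A simulation of the 2x2 model with both strata (42 per group, 6000 runs per setting) gave ratios of 0.65/0.75/0.85 at k = 1, 0.84/0.95/1.00 at k = 1.4 (ρ = 0.3/0.5/0.7), and 0.57/0.63 at k = 0.8 (ρ = 0.5/0.7). With no true effect, both interaction estimators averaged within 0.01 of zero.

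**In terms of power, at equal SDs only.** If the adjusted model has f = 0.22 and hence about 81% power at N = 168, the unadjusted change has 63%, 69% and 74% at ρ = 0.3, 0.5 and 0.7. It would need 168/0.65 ≈ 258, 168/0.75 = 224 and 168/0.85 ≈ 198 patients to match.

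**Baseline imbalance.** The interaction contrast of four means of 42 has a chance baseline imbalance with SD √(4/42) = 0.31 baseline SD. The change score carries the fraction (1 − ρk) of it into the estimate, with reversed sign. At k = 1 that is 0.22, 0.15 and 0.09 SD for ρ = 0.3, 0.5 and 0.7.

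**Log fallback.** The log is undefined on −40 to 0 for d) and −30 to 0 for e). If the change is roughly normal with mean 0, 0.5 or 1 SD, the share with no defined log is Φ(−mean/SD) = 50%, 31% or 16%, and ties at exactly zero add to this. On the integer scale, with a half-point correction and assumed mean changes of −1 to 3 points and SDs of 4 to 8, the share runs from about 27% to 65%.

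**The case against.** The case for leaving the plan alone is reasonable. Endpoints d) and e) are defined as changes and modelled as changes, so nothing in the SAP contradicts itself on the covariate. Endpoint a) needs the t1 value because its AUC does not otherwise use baseline. The unadjusted analysis is unbiased, the endpoints are exploratory, and 4.5 commits to noting clinically important baseline imbalance. The size of the gain is unknown. Patients enter fully remitted and half then discontinue, so a wider spread at t9 is at least as plausible as a narrower one. At k = 1.2 to 1.4 the intervals narrow by only 13% to 0%. All of this stands, and it makes the first part a matter of efficiency.

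It is also right that the imbalance figures are not a second harm. They are how the variance is lost, and they are already inside the ratios.

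The timing of t1 is a fair caution. Section 2.7 counts t9 as week 13 after randomisation, so t1, at week 1, appears to follow it, and patients in the open groups may already know their allocation. This does not favour the current plan, though. If that knowledge had shifted the t1 score, the change score subtracts the whole shift, while adjustment subtracts only the fraction ρk, which is smaller whenever the slope is below 1.

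On the log, the objection is that it is only a conditional sensitivity analysis for exploratory endpoints, and that 5.4 is narrower than 5.3.2. That limits the consequence. The instruction in 5.3.2 still cannot be carried out as written. A last point is that robust or bootstrap standard errors leave the point estimate unchanged and so do not show whether outliers drive it. That is correct, but they do address the effect of non-normal residuals on intervals and p-values.

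**Conclusion.** Both parts hold. The missing covariate is a avoidable loss of precision, not a bias. Its size rests on ρ and the SD ratio, which the SAP does not give, and it may be nil if the t9-on-t1 slope is near 1. The undefined log is a specification error that needs no assumption; only the share of patients affected does. It takes effect only if the residual check fails. Neither part touches the primary analysis or any confirmatory conclusion. The change should be made because it is nearly free and one prescribed step is not executable. Confidence is medium, because the gain from adjustment is unknown and the timing of the baseline score is unconfirmed.

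**What to change.** 1. **Confirm the timing first.** State whether the baseline PSS-10 and STADI state scores are taken before patients learn whether they are in an open or hidden group. The text says t1. In Table 1, whose columns are broken in the text copy, the ticks for these scales seem to stand one column before the one carrying the t1 labels (compare the PDI row). This is a point to check, not a claimed error.
2. **Covariate.** In 5.3.2, extend the baseline-covariate line to d) and e), using the score from which each change is formed. The outcome may stay the change: with baseline in the model, the group effects are identical to those for the t9 score.
3. **Fallback.** For d) and e), replace the log analysis with one that accepts non-positive values, such as robust or bootstrap standard errors. A rank-based analysis could be added if the influence of outliers is of interest.
4. **DESS AUC.** Where the log is kept, fix an offset in advance, log(x + c), in case a patient scores zero at every visit.

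The cost is one covariate line and one sentence for d) and e), a short clause for the AUC, no new data, and one degree of freedom (about 0.6% of variance at N = 168).

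### The random-intercept model for the three Posner bias scores assumes equal variances and equal correlations across emotions, with no supporting figures, check or fallback

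*SAP*

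**What the plan says.** SAP section 5.1.2 f) defines three outcomes per patient, all under high attention to faces: "difference scores between the reaction times to happy and neutral faces, sad and neutral faces, as well as fearful and neutral faces". The neutral condition is therefore common to all three.

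Section 5.3.2 analyses them together: "Linear mixed model (random intercept model) will be used with the following variables". The fixed effects are expectation (three levels), emotion (three levels), their interaction and the two stratification variables. The only random term is an intercept for patient. No residual covariance structure, emotion-specific variance or robust standard error is mentioned.

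The main interest is the expectation-by-emotion interaction. Comparisons at the level of single emotions follow: "The post-hoc comparisons between the expectation - subgroups regarding the different emotions will be addressed exploratively". Adjusted mean differences come with 95% Wald intervals. If the interaction p-value exceeds 0.15, the model is refitted with main effects only. The section adds: "The ICC (intra-class correlation) will also be reported, where appropriate".

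Sections 2.4 and 3.1 make all secondary endpoints exploratory, without multiplicity adjustment.

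**The concern.** A patient intercept with a homogeneous residual is compound symmetry: every emotion has the same variance, and every pair of emotions has the same correlation. One score concerns positive faces and two concern negative faces, so equal spread and equal correlation should not be taken for granted. The SAP offers no SDs or correlations for these scores. It plans a residual check for the ANCOVA models and a proportional-hazards check for the Cox model, but none for this one.

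The emotion-specific comparisons and the between-emotion contrasts all take their standard errors from the pooled components. If the true covariance is unequal, the errors run in opposite directions within one table: a chance difference could look convincing for the noisier emotion, and a real one could be missed for a quieter emotion.

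A second, smaller matter is the ICC. Noise in a patient's neutral reaction time enters all three scores and is absorbed by the random intercept. The ICC therefore mixes that noise with any real consistency of the patient's bias.

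**Working it through.** **Inputs.** From the SAP: three scores per patient with a shared neutral reference (5.1.2 f); random intercept only (5.3.2); 168 patients, 42 per group (2.3). The expectation factor pools the two hidden groups, so its levels have 42, 84 and 42 patients. Assumed, because the SAP gives none: all SDs, correlations and noise variances below.

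**The plan's own figure.** The SAP states no figure for this endpoint. The total of 168 for the primary analysis does reproduce: with f = 0.22, two-sided 5%, one numerator degree of freedom and four groups, 80% power needs at least 165 patients. Rounding up to equal groups gives 168, with power 80.9%.

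**Step 1: group comparison at one emotion.** With complete data the model's total variance estimates the mean of the three true variances, v̄. The true variance at emotion k is v_k. Coverage of a nominal 95% interval is approximately

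2Φ(1.96·√(v̄/v_k)) − 1.

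| Assumed SDs | v̄ | Coverage, two quieter emotions | Coverage, more variable emotion |
|---|---|---|---|
| 1, 1, 1 | 1.000 | 95% | 95% |
| 1, 1, 1.1 | (1+1+1.21)/3 = 1.070 | 95.7% | 93.5% |
| 1, 1, 1.25 | (1+1+1.5625)/3 = 1.1875 | 96.7% | 91.2% |
| 1, 1, 1.5 | (1+1+2.25)/3 = 1.4167 | 98.0% | 88.0% |

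For the last row, √(1.4167/2.25) = 0.793, so the interval for the more variable emotion is about 21% too short.

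**Step 2: between-emotion interaction contrasts.** With equal SDs of 1, the difference between two scores has variance 2(1 − ρ). The model replaces each by the mean over the three pairs.

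- Sad–fearful correlation 0.7, other pairs 0.4: variances 0.6, 1.2 and 1.2, mean 1.0. Happy-versus-sad coverage is 2Φ(1.96·√(1.0/1.2)) − 1 = 92.6%; sad-versus-fearful is 2Φ(1.96·√(1.0/0.6)) − 1 = 98.9%.
- Sad–fearful correlation 0.8: variances 0.4, 1.2 and 1.2, mean 0.933. Coverage is about 91.6% and 99.7%.

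**Step 3: the overall interaction test.** Size in simulation with groups of 42, 84 and 42 and complete data (4,000 to 6,000 runs per scenario, so the simulation error is about 0.3 percentage points):

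- equal covariances with a shared neutral reference: 5.4%, within simulation error of 5%, with emotion-specific coverage of 94.6% to 95.3%;
- fearful noise variance doubled: 5.4%; quadrupled: 6.1%;
- sad–fearful correlation 0.7: 5.7%; 0.8: 6.3%;
- true bias for happy opposed to sad and fearful: 6.5%.

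A multivariate test with unstructured covariance gave 4.8%.

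**Step 4: the ICC.** Write each score as E_k − N. Let s²_N and s²_E be the error variances of the neutral and emotional means. Let τ²_c be the true between-patient bias variance shared by all emotions, and τ²_s the part specific to one emotion. Then

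ICC = (s²_N + τ²_c) / (s²_N + τ²_c + s²_E + τ²_s).

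- Equal noise and no true differences: 1/(1+1) = 0.50.
- No true differences, s²_N/s²_E = 1/3: 0.25; ratio 3: 0.75.
- Equal noise set to 1, τ²_c = 2, τ²_s = 0: 3/4 = 0.75; τ²_c = 0, τ²_s = 2: 1/4 = 0.25.
- Happy bias opposed to sad and fearful: 0.22 in simulation.

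The value can thus lie anywhere from about 0.2 to 0.75, and 0.50 can arise with no patient differences in bias at all.

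**The case against.** The random-intercept model is a standard, clearly stated choice and contradicts nothing in the SAP. The three scores come from one task, in the same unit and under the same attention condition, and no SAP figure shows unequal spread. A shared neutral reference with equal emotional noise produces exactly the compound-symmetric structure that the model assumes, so section 5.1.2 f) partly supports the plan. The neutral term also cancels from between-emotion contrasts. The prioritised interaction test moves little, the emotion-specific comparisons are post hoc, and with complete data the main effect of expectation rests on patient means, whose variance is estimated correctly whatever the covariance across emotions. Section 5.3 requires SDs of continuous variables, which could reveal unequal spread.

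Most of this stands and limits the weight of the point. It does not remove it. Tabulated SDs do not correct an interval, pairwise correlations are not tabulated, and no rule says what follows if the spreads differ.

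A reader might infer that the ICC must be about 0.5 because of the shared reference. The SAP does not support that: 0.50 also requires equal neutral and emotional noise and no true patient differences in bias. The SAP states neither condition and gives no trial counts per face type. Where both conditions hold with the same noise for each emotion, the planned intervals are valid.

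**Conclusion.** The point holds conditionally. The model as written fixes equal variances and equal correlations over the three emotions, and the SAP neither supports, checks nor relaxes this. If the equalities hold, nothing is wrong. If they do not, interval coverage departs from 95% in both directions by the amounts shown for the assumed covariances; at an SD ratio of 1.1 the loss is small. It would go too far to conclude that the planned intervals are wrong or that the interaction test is invalid, since no figure in the SAP shows that the spreads or correlations differ.

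The ICC cannot be read simply as consistency of a patient's bias, because it contains shared neutral-face noise. This is a minor reporting matter; the SAP itself attaches no interpretation to the ICC. Overall, this is a low-cost improvement to an exploratory endpoint.

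**What to change.** In section 5.3.2, keep the fixed effects and replace the random intercept by an unstructured covariance over emotion for each patient's three scores, with Satterthwaite or Kenward-Roger degrees of freedom. Modelling the four mean reaction times (neutral included) with unstructured covariance and taking contrasts against neutral would serve equally well.

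For this endpoint, drop the ICC and report the estimated SDs and pairwise correlations, or keep it with a sentence saying that it includes noise from the shared neutral condition.

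The cost is a change of wording and one model option. The covariance has six parameters (three variances, three covariances) where the random-intercept model has two. Four more are negligible with about 168 patients and three scores each, and almost nothing is lost if the equalities hold. Fixing the structure now also avoids choosing it after the data are seen.
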